7.8 Use of an “Efficacy Subset” of Subjects

Subjects in Full Analysis Set (FAS) who complied with the protocol (i.e. no major protocol violations), who have completed at least 8 weeks of double blinded medication and who have >75% treatment compliance with the investigational product (MP-513 or placebo) during the Double-blind treatment period will form a Per-Protocol set (PPS). Major protocol deviations will be assigned during Blind Data Review Meeting (BDRM) that will be held before database lock.

Analysis based on PPS will serve as a supportive analysis for primary efficacy endpoint.

The FAS and PPS are defined in [section 8.3](#).

7.9 Active-Control Studies Intended to Show Equivalence

Not applicable to this study.

7.10 Examination of Subgroups

Exploratory sub-group analysis will be performed for the primary efficacy i.e. change in HbA1c from baseline to Week 24 for following subgroups:

- Gender (male and female)
- Body Mass Index (BMI) ($<20 \text{ kg/m}^2$, $20 \leq \text{BMI} <25 \text{ kg/m}^2$, $25 \leq \text{BMI} <30 \text{ kg/m}^2$, $\text{BMI} \geq 30 \text{ kg/m}^2$)
- Age (<40 years, $40 \leq \text{Age} <50$ years, $50 \leq \text{Age} <60$ years, $60 \leq \text{Age} <70$ years, $\text{Age} \geq 70$ years, $\text{Age} <65$ years and $\text{Age} \geq 65$ years)
- Alcohol history (Abstainer, >28 units of alcohol per week and ≤ 28 units of alcohol per week)
- Baseline HbA1c ($<7.0\%$, $7.0\% \leq \text{HbA1c} <8.0\%$, $8.0\% \leq \text{HbA1c} <9.0\%$, $\text{HbA1c} \geq 9.0\%$)
- Baseline FPG ($<130 \text{ mg/dL}$, $130 \text{ mg/dL} \leq \text{FPG} <160 \text{ mg/dL}$, $160 \text{ mg/dL} \leq \text{FPG} <200 \text{ mg/dL}$, $\text{FPG} \geq 200 \text{ mg/dL}$)
- Duration of diabetes (<1 year, $1 \leq \text{Duration} <5$ years, $5 \leq \text{Duration} <10$ years, $\text{Duration} \geq 10$ years)

8 STATISTICAL ANALYSIS

8.1 Disposition of Subjects

The number and percentage of subjects randomized, completed, and discontinued during the study, as well as the reasons for all post-randomization discontinuations, will be summarized by treatment groups. The number of placebo run-in subjects who do not meet randomization criteria will also be presented in the disposition summary table.

A listing of all subjects who discontinued the study after randomization and placebo-run in subjects who do not meet randomization criteria will be provided. This will also include the specific reason for discontinuation.

8.2 Protocol Deviations

Potential deviations will be identified prior to database lock.

All protocol deviations will be reviewed in a blinded fashion during the blind review of the data and will be described in more detail in the minutes of blind data meeting. The sponsor review team will approve all the final protocol deviation assignments. Once all protocol deviation determinations are finalized and approved, the database will be locked and the treatment codes will be unblinded for statistical analysis.

Number and percentage of subjects with at least one major protocol deviations will be summarized by treatment group and overall.

A listing of all major protocol deviations by subjects to determine reasons for exclusion from the FAS and PPS will be presented.

8.3 Analysis Populations

The study will use following analysis populations for data summarization. Number and percentage of subjects in each analysis set will be summarized by treatment group and overall.

Table 6: Analysis Population

Population	Definition	Displays	Note
All Subject Set	The All Subject Set includes all subjects who were screened	Displays on subject disposition	The subjects will be analyzed for disposition
Randomized Set	The Randomized Set includes all subjects who were randomized	Displays on subject population and	The subjects will be analyzed according to the treatment to which they were randomized to, irrespective of treatment received
Full Analysis Set (FAS)	The FAS includes all subjects in the randomized set who have received at least one dose of study medication during the double-blind treatment	Displays related to demography, other baseline characteristics and	The subjects will be analyzed according to the treatment to which they were randomized

Population	Definition	Displays	Note
	period and have at least one post-baseline efficacy observation. Subjects who were not diagnosed with type 2 diabetes mellitus will be excluded.	all efficacy analyses	to, irrespective of treatment received
Per-Protocol Set (PPS)	The PPS includes subjects in the FAS who have no major protocol violations, who have completed at least 8 weeks of double-blinded medication and who have > 75% treatment compliance with the investigational product (MP-513 or placebo) during the Double-blind treatment period.	Demographics and Primary efficacy analysis	All protocol violations will be defined in more detail in the blind review document at a Blind Data Review Meeting that will be held before database lock. The subjects will be analyzed according to the treatment to which they were randomized to, irrespective of treatment received.
Safety Analysis Set	The Safety Analysis Set includes all subjects in the randomized set who have received at least one dose of study medication during the double-blind treatment period.	Displays related to demography, other baseline characteristics and all safety analyses	The subjects will be analyzed as MP-513 if the subjects received MP-513 at least once, irrespective of treatment to which they were randomized to. In other cases, the subjects will be analyzed according to the treatment they were randomized to.

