1.2. Protocol Synopsis

Sponsor: Mitsubishi Tanabe Pharma Corporation	Name of Medical Product: MP-513	Active Ingredient(s): Teneligliptin
Study Centre(s): Multi-centre study that will be conducted in approximately 35 sites in China		
Study Duration: 30 weeks (2 weeks screening, 2 weeks placebo run-in, 24 weeks treatment, 2 weeks follow-up) The study period is estimated to start from [REDACTED] to [REDACTED].		Study Phase: 3
Study Title: A phase 3 randomized, double-blind, placebo-controlled parallel group efficacy and safety monotherapy study of MP-513 in Chinese subjects with type 2 diabetes mellitus inadequately controlled with diet and exercise		
Study objectives: To evaluate the efficacy and safety of MP-513 compared with placebo in Chinese subjects with type 2 diabetes mellitus inadequately controlled with diet and exercise		
Methodology: Multi-centre, randomized, double-blind, placebo-controlled, parallel-group study		
Number of Subjects (Planned): 240 subjects (120 subjects to MP-513 and 120 subjects to placebo)		
Diagnosis and Inclusion Criteria: The subjects have to meet all of the following inclusion criteria: 
 1. A signed and dated informed consent form has been obtained from the subject, in accordance with International Conference on Harmonisation guidelines on Good Clinical Practice (ICH GCP), before any screening or study related procedures take place. 2. The subject is aged ≥ 18 years at signature of the informed consent form 3. Hospitalization status: outpatient 4. The subject has had a documented diagnosis of type 2 diabetes mellitus for at least 3 months at the screening visit (Day -28) 5. The subject is undergoing diet and exercise therapy, and diet and exercise regimen has not been changed for at least 8 consecutive weeks at the screening visit (Day -28). Subjects who cannot do exercise due to complication are not limited to this criteria. 6. The subject's glycosylated fraction of haemoglobin (HbA1c) is $\geq 7.0\%$ and $< 10.0\%$ at the screening visit (Day -28) and on Day -14. 7. The subject's fasting plasma glucose (FPG) is < 270 mg/dL (15 mmol/L) at the screening visit (Day -28) and on Day -14. 8. The subject is capable of giving informed consent, complying with the restrictions and requirements of the protocol and, in the opinion of the investigator, will be able to complete the study. 		

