The placebo-subtracted change in HbA1c from baseline at Week 12 was $-0.79 \pm 0.07\%$ (Least squares mean \pm standard error [LS mean \pm SE]). There were no serious adverse events (SAEs) in the MP-513 group but 4 SAEs observed in 4 subjects in the placebo group. There were no significant differences in the incidences of adverse events (AEs) and adverse drug reactions (ADRs) between the placebo and MP-513 groups.

A phase 3, combination therapy study with sulfonylurea (3000-A6) was conducted in subjects with type 2 diabetes mellitus to evaluate efficacy and safety of MP-513 20 mg versus placebo for 12 weeks (double-blind period). The safety and efficacy of MP-513 20 mg for following 40 weeks are also evaluated (open-label period).

In the double-blind period, the placebo-subtracted change in HbA1c from baseline at Week 12 was $-1.00 \pm 0.08\%$ (LS mean \pm SE). There was no significant difference in the incidences of AEs and ADRs between the placebo and MP-513 groups.

In open-label period, although all subjects received MP-513 for another 40 weeks following the double-blind period, the incidence of AEs was not demonstrated increasing tendency in association with the prolonged treatment period. There were 10 SAEs in 7 of 96 subjects (7.3%) in the MP-513 group (weeks 0 to 52) and 5 SAEs in 4 of 98 subjects (4.1%) in the placebo group (weeks 0 to 52). The result also suggested that the HbA1c lowering effect of MP-513 was maintained throughout the study.

A phase 3, combination therapy study with thiazolidinedione (3000-A7) was conducted in subjects with type 2 diabetes mellitus to evaluate efficacy and safety of MP-513 20 mg versus placebo for 12 weeks (double-blind period). The safety and efficacy of MP-513 20 mg for following 40 weeks are also evaluated (open-label period).

In the double-blind period, the placebo-subtracted change in HbA1c from baseline at Week 12 was $-0.74 \pm 0.06\%$ (LS mean \pm SE). The incidences of AEs and ADRs were significantly higher in the MP-513 group (61.2% and 11.7%, respectively) than in the placebo group (46.5% and 2.0%, respectively).

In the open-label period, although all subjects received MP-513 for another 40 weeks following the double-blind period, an increasing incidence of AEs was not demonstrated in association with the prolonged treatment period. There were 12 SAEs in 11 of 103 subjects (10.7%) in the MP-513 group (weeks 0 to 52) and 6 SAEs in 4 of 101 subjects

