8.8 Analysis of Safety

All safety data will be summarized by treatment groups using the Safety Analysis Set. No formal statistical test would be performed to determine statistical significance between treatment groups.

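### The column rule for the Safety Analysis Set counts a subject randomised to MP-513 who took only placebo as MP-513, although that subject was never exposed

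*SAP*

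**What the plan says.** SAP 8.3, Table 6, defines membership of the set by any double-blind dose: "The Safety Analysis Set includes all subjects in the randomized set who have received at least one dose of study medication during the double-blind treatment". A placebo tablet counts as such a dose.

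The note to the same row then assigns each member to a treatment column in two steps. The first is by exposure: "The subjects will be analyzed as MP-513 if the subjects received MP-513 at least once, irrespective of treatment to which they were randomized to". The second covers everyone left over: "In other cases, the subjects will be analyzed according to the treatment they were randomized to".

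SAP 8.8 applies the set throughout: "All safety data will be summarized by treatment groups using the Safety Analysis Set". It also makes the comparison descriptive: "No formal statistical test would be performed to determine statistical significance between treatment groups".

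The protocol's definition of the set (section 6.9.1.3) deals with membership only and has no rule for columns. It also requires a post-baseline safety observation, which the SAP does not. In SAP Table 6 the FAS and the Per-Protocol Set are analysed by randomised arm.

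**The concern.** The first step of the note sets the randomised arm aside in favour of actual exposure, so the evident aim is to tabulate safety by treatment received. The second step goes back to the randomised arm. There are only two products, so a member of the set who never took MP-513 took only placebo. If that subject was randomised to placebo, the second step gives the right column. If the subject was randomised to MP-513 and was given placebo by a kit error, it does not.

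An unexposed subject then sits in the MP-513 denominator, and any event that subject has is reported as an event on MP-513. SAP 6.8.1.1 and 6.8.1.2 add to this, because a missing causality assessment is counted as drug-related. Such an event could therefore appear as an adverse drug reaction to a drug the subject never took. The lines most sensitive to this hold few subjects, such as serious ADRs or ADRs leading to discontinuation (SAP 8.8.1).

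**Working it through.** The documents give no figure on this point, so there is nothing to reproduce. The check has two parts: a listing of cases, then the arithmetic per misplaced subject.

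**Step 1: every combination of randomised arm and treatment received.**

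| Randomised | Received | Column under SAP rule | Column by treatment received* | Agree? |
|---|---|---|---|---|
| MP-513 | MP-513 only | MP-513 | MP-513 | yes |
| MP-513 | placebo only | MP-513 | placebo | **no** |
| MP-513 | both | MP-513 | MP-513 | yes |
| placebo | MP-513 only | MP-513 | MP-513 | yes |
| placebo | placebo only | placebo | placebo | yes |
| placebo | both | MP-513 | MP-513 | yes |

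*Any MP-513 counts as MP-513.

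Four rows involve a wrong kit: rows 2, 3, 4 and 6. Three of the four are placed correctly.

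**Step 2: what one such subject does to an MP-513 percentage.** Inputs: 120 subjects per arm (Protocol 1.2), of whom one, randomised to MP-513, took only placebo. The correct MP-513 denominator is then 119, and the SAP rule makes it 120. Let x be the number of events among the 119 exposed subjects.

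- Subject has no event: x/119 becomes x/120.
  - x = 1: 0.840% becomes 0.833%, a fall of 0.007 points.
  - x = 12: 10.08% becomes 10.00%, a fall of 0.08 points.
- Subject has the event: x/119 becomes (x + 1)/120.
  - x = 0: 0% becomes 0.83%, a rise of 0.83 points.
  - x = 1: 0.84% becomes 1.67%, a rise of 0.83 points.
  - x = 12: 10.08% becomes 10.83%, a rise of 0.75 points.

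In general the fall is p/120 and the rise is (1 − p)/120, where p = x/119. A fall of 0.01 to 0.1 points therefore corresponds to lines of about 1% to 12%. On a very common line it is larger: at p = 61.2% it is 61.2/120 = 0.51 points.

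**Step 3: the expected shift.** Let k subjects randomised to MP-513 take only placebo. The documents give no value for k, so 1 to 12 is an assumed range. The expected MP-513 percentage under the SAP rule is

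((120 − k) × p_MP + k × p_placebo) / 120,

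which differs from p_MP by −(k/120) × (p_MP − p_placebo).

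For illustration only, take the rates of the earlier thiazolidinedione combination study 3000-A7 (Protocol section 4), where AE and ADR incidences were "significantly higher in the MP-513 group (61.2% and 11.7%, respectively) than in the placebo group (46.5% and 2.0%, respectively".

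| k | ADR, MP-513 column (by treatment received: 11.70%) | AE, MP-513 column (by treatment received: 61.20%) | Risk difference shrinks by k/120 |
|---|---|---|---|
| 1 | (119 × 11.7 + 1 × 2.0)/120 = 11.62% | (119 × 61.2 + 1 × 46.5)/120 = 61.08% | 0.8% |
| 3 | 11.46% | 60.83% | 2.5% |
| 12 | 10.73% | 59.73% | 10% |

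For k = 1 the expected shift is −0.08 points for ADRs and −0.12 points for AEs. If the two rates are equal it is zero. If the event is rarer on MP-513, the sign reverses and the MP-513 percentage goes up.

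**The case against.** The case against giving this much weight is strong on consequence, though not on the reading of the rule.

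- **The case is remote.** Kits are assigned through the IWRS (Protocol 6.4.2) and double-blind medication is dispensed at six visits, the randomisation visit and Visits 1 to 5. A subject must have had placebo at every dispensing, or have stopped early after a wrong kit. The documents give no reason to expect even one. This stands.
- **Nothing inferential depends on it.** Safety is descriptive and the efficacy sets use the randomised arm. This also stands.
- **Existing listings would help.** Major deviations are listed by subject (SAP 8.2) and all CRF data are listed (SAP 7.1). These might reveal a wrong kit, but they do not change the column, and the deviation listing is tied to exclusions from the FAS and PPS.
- **The second step may have been meant for subjects whose actual kit cannot be established.** That would be a reasonable default, but the note does not limit itself to them.

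A reader might infer three stronger things, and the documents support none of them.

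1. That the rule systematically dilutes MP-513 event rates. It does so in expectation only for events more frequent on MP-513, and an individual subject with an event moves the percentage up.
2. That dilution amounts to 0.8 points per subject. That figure is the size of the upward move when the subject has the event. The downward move is about 0.01 to 0.1 points on lines of 1% to 12%.
3. That the rule breaks down whenever there is a dispensing error. Three of the four wrong-kit combinations are handled correctly, including a placebo-randomised subject who is exposed to the drug.

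**Conclusion.** The point holds as a narrow wording error. On the plain text, a subject randomised to MP-513 who took only placebo is tabulated as MP-513, and nothing in the protocol or elsewhere in the SAP overrides this. It is a stated rule with a wrong result in one case, not a missing detail.

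The consequence is small. It is zero if no such error happens. Otherwise a single subject matters mainly on a rare-event line, where one event would be charged to a drug not taken. The sizes in the working assume the planned 120 per arm. The expected shifts also borrow rates from an earlier combination study that are not this trial's assumptions. No test, error rate or efficacy result is touched. The correction is desirable but not critical.

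**What to change.** In SAP 8.3, Table 6, replace the last sentence of the Safety Analysis Set note with: *All other subjects in the set, having received only placebo in the double-blind period, will be analysed as placebo.* Keep the first sentence as it is.

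Add a listing, or a flag in an existing one, of every subject whose analysed arm differs from the randomised arm, with the dates of the wrong kit. If a default is wanted for subjects whose actual kit cannot be established, state it separately and confine the randomised-arm rule to them.

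The cost is one sentence and one listing, with no effect on data collection, sample size or the efficacy analyses. It should be settled before unblinding, because a change of column afterwards could look data-driven.

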8.4 Demographic and Other Baseline Characteristics

Demographic and baseline characteristics will be summarized using the FAS, PPS and safety populations. No formal statistical test would be performed to determine statistical significance between treatment groups.

8.4.1 Demographics

Age, height, body weight (at screening) and body mass index (BMI) in kg/m^2 will be summarized as continuous variables by treatment group and overall using descriptive statistics.

Gender and race will be summarized as categorical variables by treatment group and overall using frequency counts and percentages.

Duration of diabetes mentioned in [section 6.4](#) will be summarized descriptively by treatment groups and overall.

Alcohol history will be categorized as:

- Abstainer
- ≤ 28 units of alcohol per week
- > 28 units of alcohol per week

These will be summarized by treatment group and overall using frequency counts and percentages.

All demographic characteristics will be presented in full subject listings.

8.4.2 Medical History

A full subject listing of medical history will be presented.

8.5 Prior and Concomitant Therapy

A full subject listing of prior and concomitant medications will be presented.

8.6 Extent of Exposure and Compliance to Study Treatment

Extent of Exposure and Compliance to Study Treatment will be summarized using the FAS, PPS and safety populations.

Duration of study drug exposure during the double blind treatment period and treatment compliance during the double blind treatment period will be calculated as mentioned in [section 6.6](#) and will be summarized descriptively.

The treatment compliance during double blind period will also be summarized for compliance $\leq 75\%$ and $>75\%$ using frequency counts and percentages.

8.7 Analysis of Efficacy Parameters

All efficacy analysis will be performed on FAS unless otherwise stated.

A full subject listing will be presented for efficacy results (HbA1c, FPG, fasting insulin, C-peptide, glucagon, HOMA-IR, HOMA- β and body weight).

8.7.1 Analysis of Primary Efficacy Variable

8.7.1.1 Primary Analysis of Primary Efficacy Variable

The primary efficacy endpoint is to evaluate the change in HbA1c from baseline to Week 24 in the group receiving MP-513 compared with the group receiving placebo in Chinese subjects with type 2 diabetes mellitus inadequately controlled with diet and exercise. The reduction in HbA1c value indicates improvement.

The primary efficacy will be assessed by testing the null hypothesis that, there is no difference in the change in HbA1c from baseline to Week 24 in the group receiving MP-513 compared to the group receiving Placebo. In statistical notation the hypothesis is defined as follows:

Null Hypothesis $H_0: \mu_{MP-513} = \mu_{Placebo}$

Alternate Hypothesis $H_A: \mu_{MP-513} \neq \mu_{Placebo}$

Where μ_{MP-513} : Mean change in HbA1c from baseline at week 24 for MP-513

μ_{Placebo} : Mean change in HbA1c from baseline at week 24 for placebo

The missing HbA1c values at week 24 will be imputed using LOCF approach prior to analysis. The change in HbA1c from baseline to Week 24 (LOCF) will be analysed using analysis of covariance (ANCOVA) with treatment as a fixed effect and baseline value as a covariate in the model.

For the treatment effects and the difference between the treatment groups, the least square means from ANCOVA will be presented along with the corresponding SE and CI. The treatment difference in mean change from baseline will be computed using the model. The p-values for the test of significance, SE and CI of the mean difference will be presented.

The change in HbA1c from baseline for all the post baseline assessments visits, Week 12 (LOCF) and Week 24 (LOCF) will also be summarized as continuous variable using descriptive statistics.

The line graph for mean change in HbA1c from baseline to Week 24 and Week 24 (LOCF) will be presented. The 95% CIs will also be shown in the graph with error bar. The plots of Week 24 and Week 24 (LOCF) will not be connected.

8.7.1.2 Supportive Analysis of Primary Efficacy Variable

The study will have two supportive analyses to be performed on primary efficacy variable i.e. change in HbA1c from baseline to Week 24, as follows:

- The change in HbA1c from baseline to Week 24 in MP-513 compared to Placebo will be performed on PPS using the same statistical methodology as described for the primary analysis.

The change in HbA1c from baseline to Week 24 in MP-513 compared to Placebo will be analysed using mixed effects model for repeated measure (MMRM), with treatment, visit and interaction of treatment and visit as fixed effects and baseline value as a covariate in the model. An unstructured covariance matrix will be used to model the covariance of within-subject values. The Kenward-Roger approximation will be used to estimate denominator degrees of freedom (Kenward and Roger, 1997). For this analysis, missing data will not be imputed, i.e. only the observed data will be used.

